7.2 Adequacy of Protection Against Risks

Subjects will be encouraged to report any discomforts during testing and any illness or change in wellbeing immediately to the local site PI or study coordinator at any time during the study. The following protection against risks are in place:

- i. Phlebotomy: Sterile technique followed by brief compression and utilization of trained phlebotomists will minimize risk of infection or bleeding. ELA-Max cream or an over-the-counter numbing cream (e.g., Anusol) can be applied to minimize pain. Participants will rest in bed or chair while phlebotomy is performed to ensure safety. Phlebotomy will be collected at Colorado State University (CSU; Site 1) in the Human Performance/Clinical Research Laboratory, at Children's Hospital Colorado (CHCO; Site 2) in the Pediatric Clinical and Translational Research Center (CTRC), at the Uniformed Services University (USU; Site 3) in the Military Cardiovascular Outcomes Research (MiCOR) program, and at Children's National Medical Center (CNMC; Site 4) in the Clinical Research Unit. All units are familiar with blood drawing and equipped to perform far more complex procedures (e.g., intravenous glucose testing, clamps, biopsies, etc.) than the fasting and two-hour blood draws proposed in the current protocol. In addition, a physician or advanced practice provider will always be on call.

- ii. Emotional assessments, monitoring, and referrals: It is anticipated that within samples comprised of adolescents with overweight/obesity and elevated depression symptoms, there will be participants who develop more severe depressive symptoms or suicidal ideation or behavior. Should a participant demonstrate signs of active suicidal ideation or suicidal behavior or worsening depression or mental health, referrals to mental health providers will be provided. All participants are carefully debriefed and written procedures for managing risk and safety circumstances (e.g., suicidality) are in place. During the baseline screening, if the KSADS-COMP interview assessment reveals current suicidal ideation or self-harm or if parents/teens reports a current exclusionary mental health diagnosis, the participant will be referred for treatment and excluded from the study. During the active intervention phase, participants' mood will be monitored weekly on a mood monitoring form that includes an assessment of suicidal ideation. During the 6-week and 1-year follow-ups, the KSADS-COMP is re-administered to assess for suicidality/self-harm. All research KSADS-COMP interviewers and MBI, CBT, and HealthEd interventionists will be trained to assess suicidal intent, plan and possible method, and they will discuss this assessment with a clinical psychologist supervisor at each site. A specific, detailed protocol is in place for addressing concerns about worsening mood or reports of suicidality. If indicated, a treatment referral will be facilitated with the participant and the family. If the participant is in need of an urgent evaluation (e.g., is actively suicidal with a plan and intent to carry out such actions), she or he will be immediately referred to the nearest emergency department until the participant can be safely referred for outside treatment as recommended.

Based upon our prior studies,^{56,57,100,119} we anticipate that depression symptoms will improve in both MBI and CBT, with potentially greater improvements in MBI. We also anticipate that depression symptoms will improve in adolescents assigned to HealthEd, but to a lesser extent than adolescents in MBI and CBT. CBT is a treatment of choice for prevention and treatment of depression,¹⁷⁴ and the particular CBT manualized program used in this study has demonstrated efficacy and effectiveness in reducing depression symptoms and preventing future MDD occurrence in adolescents over a 1-2 year follow-up.¹²³⁻¹²⁵ MBI has less research evidence, particularly for long-term follow-up/duration of effects, but our preliminary data support the possibility that the particular manualized intervention proposed in this trial, Learning to BREATHE, may be superior to CBT, for decreasing depression symptoms at post-treatment and up to 1 year later.^{100,101} Adolescents recruited for participation in the current, proposed study will have elevated depression symptoms, but will not report a psychiatric diagnosis that, in the opinion of the study investigators, necessitates treatment. Likewise, adolescents will not be enrolled who report current active suicidality or self-harm. Most adolescents with subthreshold depression symptoms, as well as the majority of adolescents with depression disorders like MDD, do not seek or obtain treatment. Thus, participation in the study holds the prospect, regardless of condition, of increased monitoring than would be likely if adolescents did not participate.

- iii. Physical assessments, monitoring, and referrals: During the baseline screening, if assessments reveal a physical health problem (e.g., T2D), the participant will be referred for treatment and excluded from the study. Eligible adolescents who proceed to enrollment/randomization will be identified as being at risk for developing T2D, but they will not have current T2D. The vast majority of adolescents at-risk for T2D do not receive interventions to reduce their risk of developing T2D. Intensive, structured lifestyle interventions in clinical trials have demonstrated some short-term

success in adolescents, but typically have limited sustainability and poor adherence.²⁴ Thus, adolescents who are randomly assigned to the attention- and time-matched didactic control condition, HealthEd, will receive more support and psychoeducation than they would very likely receive if they did not participate in the study. Our preliminary data also are suggestive of the possibility that CBT and MBI (Learning to BREATHE) may improve or prevent the worsening of insulin resistance.^{56,57,100}

- iv. Vulnerable subjects: Adolescent minors (ages 12-17 years) are included as vulnerable subjects in the proposed study. In the absence of sufficient evidence-based programs to address the major public health problems of obesity and cardiometabolic disease in adolescents, there is a strong need for the scientific advancement of targeted therapies that jointly address depression and insulin resistance as the main precursor to T2D. The PI, Co-investigators, and the expert Consultants are experienced in working with minors. The research of key members on the investigative team, to date, has primarily focused on this vulnerable population in an effort to intervene prior to adulthood, at a time when the course of depression and insulin resistance is more malleable. Study staff will be thoroughly trained in identifying any emotional or physical distress or discomfort and will be instructed to terminate the protocol if a participant demonstrates distress. Study staff will emphasize to participants that they are able to withdraw from the study at any time, without penalty.

7.3 Specification of Safety Parameters

The following key measures and corresponding parameters will guide risk/safety handling:

- i. Oral glucose tolerance testing (OGTT): OGTT is conducted at three time points during the course of the study, including screening/baseline, 6-week follow-up, and 1-year follow-up. If an adolescent has impaired fasting glucose (fasting glucose ≥ 100 mg/dL), impaired glucose tolerance (2-hour OGTT glucose ≥ 140 mg/dL), or with values potentially suggestive of T2D (fasting glucose ≥ 126 mg/dL or 2-hour OGTT glucose ≥ 200 mg/dL) based upon immediate glucose analysis (e.g., StatStrip), they and their parent/guardian will be notified and referred to the primary care physician for follow-up. Those adolescents with T2D at baseline will be excluded. Adolescents with impaired fasting glucose or impaired glucose tolerance will not be excluded, but they and their families will be notified at baseline as well as any follow-up assessment.
- ii. Medical history/physical exam: A medical history is conducted at baseline/screening and updated at the 6-week and 1-year follow-up. A review of physical health is conducted at all three of these intervals, with pubertal staging only at baseline/screening and repeated at 1-year if a physician/provider reported adolescent to be below tanner staging 5 at baseline. Any adolescent with a major medical problem or taking medications that could interfere with safety or validity, at baseline, will not be included. Any adolescent with a current exclusionary mental health diagnosis reported by parents and/or adolescents will not be included. Physicians/medical providers at each site will review medical histories during the follow-up interval and if any medical condition develops that was not present at baseline, will refer families for medical treatment, as indicated. Likewise, psychologists will refer families for psychological treatment, as indicated.
- iii. Schedule for Affective Disorders and Schizophrenia for School-Aged Youth – Computerized Version (KSADS-COMP) – Suicidality/self-harm module and mood monitoring: The KSADS-COMP semi-structured clinical interview – Suicidality and Self-harm Module is conducted at three time points during the course of the study, including screening/baseline, 6-week follow-up, and 1-year follow-up. Mood monitoring is carried

out during the 6-week intervention phase, with adolescents completing a mood monitoring form at each intervention session, in all conditions (MBI, CBT, and HealthEd). As determined on the KSADS-COMP, adolescents who have, at baseline, active suicidal ideation or self-harm—a discreet marker of depression severity—will not be studied. The KSADS-COMP administered at the two follow-ups re-assesses suicidality/self-harm and in the event that an adolescent develops a suicidality or self-harm at either follow-up, the adolescent and parent/guardian will be notified and treatment referrals will be provided as indicated.

7.4 Adverse Events and Serious Adverse Events

7.4.1 Adverse Events

An **adverse event** is defined as any unfavorable and unintended diagnosis, symptom, sign (including an abnormal laboratory finding), syndrome or disease which either occurs during the study, having been absent at baseline, or if present at baseline, appears to worsen. All adverse events will be recoded regardless of their relationship to the study intervention (i.e., study and non-study related adverse events, as well as expected and unexpected adverse events).

7.4.2 Serious Adverse Events

A **serious adverse event** is defined as any untoward medical occurrence that results in death, is life threatening, requires inpatient hospitalization or prolongation of existing hospitalization, results in persistent or significant disability/incapacity, or is a congenital anomaly.

7.4.3 Adverse Events Reporting

All adverse events, including serious and non-serious, expected and unexpected, will be reported to the IRB at the annual continuing reviews in the form of electronic data sheets or summary language. Serious adverse events will be reported by the PI verbally and in writing as soon as possible to the IRB, IMC, and NCCIH, with a maximum of 7 calendar days for death or life-threatening adverse events, and within 15 calendar days for all other serious adverse events. All site PIs will be responsible for monitoring adverse events at their respective sites and if serious events arise, reporting this immediately to the study PI [name].

Adverse event forms will be completed by study coordinators on a form which is saved on REDCap or a secure server, which can only be accessed by site personnel using a username and password.

7.5 Follow-up for Adverse Events

All adverse events will be reviewed at a weekly coordinators meeting, run by the lead study coordinator and attended by all four local site coordinators (CSU, CHCO, USU, and CNMC), as well as at a monthly all hands investigator/staff team meeting. For expected adverse events (e.g., development of MDD, suicidal ideation, or T2D), we will follow protocol and risk/safety management plans, as outlined in **section 7.3 of this protocol**. For any unexpected, study-related events, we will use a team-based approach to problem solve a resolution that minimizes the likelihood of the event recurring.

7.6 Safety Monitoring

We have formed an independent monitoring committee (IMC) comprised of three individuals who are not part of the proposed research and who have experience in the conduct and analysis of clinical trials. [name] is a physician with expertise in adolescent obesity and type 2 diabetes; [name] is a clinical psychologist with expertise in adolescent

depression and diabetes; and [name] is a biostatistician who has experience in randomization, monitoring, and analysis of clinical trials.

In the start-up phase of the study (Year 1, Quarters 1-2), we will convene an initial meeting with the IMC, including the PI [name] (CSU) and the study statistician, [name], to discuss and establish the complete and detailed data safety and monitoring plan (DSMP). The investigative leads at each side (i.e., Drs. [name], [name], and [name]) will review the DSMP and be available for consultation and questions. Specifically, we will review the protocol methods, steps that will be taken to monitor and maintain confidentiality of data, consent documents, all risks and protections to participants, and qualitative and quantitative data analytic plans. We will review expected adverse events and planned steps to minimize risks, and we will discuss the timeline for reporting of serious adverse events and non-serious adverse events to the IMC and IRB. Additionally, we will specify stopping rules.

Following the initiation of recruitment, a report will be prepared every 6 months by [name] and [name], with administrative support from the multisite coordinator, which will include information regarding timeline/milestones, participant recruitment, accrual, and attrition by condition and site, potential adverse events by condition and site, summary statistics for key variables by site, including reports of any missing data, preliminary analyses of fidelity, feasibility, and acceptability, as they become available, and any other issues or unanticipated problems or challenges that may have arisen during the course of the study.

The IMC will convene every 6 months to provide feedback on the progress of the study as well as assistance in approaching any potential difficulties that may arise. More frequent meetings will be scheduled as needed. [name], as well as the statistician and investigative leads at each site, will be available to attend IMC meetings to answer questions during an open session, prior to the IMC's private deliberation. The role and responsibilities of the IMC will include: reviewing the protocol and the DSMP; considering any possible major changes to the protocol; evaluating the progress of the study, including assessments of data quality, timeliness, recruitment, retention, and participant risk vs. benefit; reviewing serious adverse events; and considering modifications to the study protocol based upon progress. The IMC will issue a formal memo, signed by all members of the IMC, at the conclusion of their deliberations. All reports prepared by the study team for the IMC and all memos issued by the IMC on the progress of the study will be provided to NCCIH.

8. STATISTICAL CONSIDERATIONS

8.1 General Design Issues

The current project is a pilot randomized controlled trial implemented at four sites with three arms. In line with the NCCIH U01/R01 grant mechanism, the purpose of the project is to gather information for use in designing a subsequent trial to compare the efficacy of the three arms.

8.2 Sample Size and Randomization

Aim 1: Assuming that the true proportion of sessions within an intervention arm during which fidelity criteria are met is 85%, $p=0.06$,¹⁷⁵ 4 clusters (one facilitator per treatment arm per site), 16 sessions per cluster, and coefficient of variation of the number of sessions equal to 0.01, then the width of the 95% CI is 24%. This estimate indicates that we will have reasonable precision in our estimates of fidelity after accounting for the intraclass correlation coefficient (ICC).

Aim 2: Assuming that the true proportion of loss to follow up within an intervention arm is 15%, $p=0.06$, 4 clusters, an average of 8 participants per cluster, and coefficient of variation of the

number of participants equal to 0.11, then the width of the 95% CI is 28%. In the original power calculations, the width of the 95% CI was 26%, so we will still have reasonable precision in our estimates of loss to follow up after accounting for the ICC.

8.3 Definition of Populations

The intent-to-treat sample will be all adolescents who are randomized (N=120).

8.4 Interim Analyses and Stopping Rules

Given the pilot nature of this study, no interim analyses or stopping rules are planned outside of the outcomes listed subsequently in **sections 3 and 8.5**. Analyses of primary and secondary outcomes will be conducted when all data for the respective outcomes have been collected. In line with NCCIH's recommendations, no analyses of outcomes will be carried out prior to study completion.

8.5 Outcomes

[name] is the study biostatistician and she will be responsible for conducting the analyses of this pilot trial and discussing those results at the all hands investigator/staff monthly meeting. [name] is the study qualitative expert and she will be responsible for overseeing the analyses of the focus groups with adolescents and focus groups with study personnel. [name] will present these results for discussion, as they become available, at the all hands investigator/staff monthly meeting.

8.5.1 Primary Outcome

The primary outcomes for each study aim are:

Aim 1: Test multisite fidelity of training/implementation of 6-week group MBI, CBT, and HealthEd to adolescent girls and boys at-risk for T2D with depression symptoms		
Objective	Endpoint	Metric; Analysis
Intervention Fidelity (Primary)	12-months	Facilitators score ≥ 8 on adherence and competence ratings of MBI, CBT, and HealthEd adolescent group sessions (1=poor to 10=exceptional)

Aim 2: Evaluate multisite feasibility/acceptability of recruitment, retention, and adherence for a protocol involving randomization to 6-week group MBI, CBT, or HealthEd with 6-week and 1-year follow-up		
Objective	Endpoint	Metric; Analysis
Recruitment Feasibility (Primary)	12-months	$\geq 80\%$ eligible adolescents will enroll

8.5.2 Secondary Outcomes

The secondary endpoints for each aim are:

Aim 1: Test multisite fidelity of training/implementation of 6-week group MBI, CBT, and HealthEd to adolescent girls and boys at-risk for T2D with depression symptoms		
Objective	Endpoint	Metric; Analysis
Training Fidelity (Secondary)	6-months	Facilitators score $\geq 80\%$ on post-training knowledge/competency tests of MBI, CBT, and HealthEd

Training Fidelity (Secondary)	6-months	Facilitators score ≥ 8 on adherence and competence ratings of MBI, CBT, and HealthEd mock group sessions (1=poor to 10=exceptional)
Aim 2: Evaluate multisite feasibility/acceptability of recruitment, retention, and adherence for a protocol involving randomization to 6-week group MBI, CBT, or HealthEd with 6-week and 1-year follow-up		
Objective	Endpoint	Metric; Analysis
Recruitment Feasibility (Secondary)	12-months	Attainment of target $N=120$ within a 12-month period; CONSORT flow/number of months to reach recruitment goal
Intervention Feasibility (Secondary)	6-weeks	$\geq 80\%$ adolescents attend 5:6 (80%) group MBI/CBT/HealthEd sessions
Intervention Acceptability (Secondary)	6-weeks	$\geq 80\%$ adolescent liking/credibility ratings ≥ 4 (1=not at all to 5=extremely)
Intervention Acceptability (Secondary)	6-weeks	Themes indicative of acceptability of interventions, as derived from grounded theory/qualitative analysis of adolescent focus-groups at post-intervention
Retention Feasibility (Secondary)	12-months	$\geq 80\%$ at post-treatment follow-up and $\geq 70\%$ at 1-year follow-up
Assessment Feasibility (Secondary)	18-months	$\geq 95\%$ accuracy on standardized protocol checklists for all assessments

8.6 Data Analyses

8.6.1 Primary Analyses

In Aim 1, descriptive analyses will be conducted to: (i) describe post-training knowledge/competency of MBI, CBT, and HealthEd to determine if facilitators score $\geq 80\%$; (ii) describe adherence and competence ratings of mock group sessions of MBI, CBT, and HealthEd to determine if ratings ≥ 8 (1-10 scale with 10 being the most positive valence); and (iii) describe adherence and competence ratings of pilot group sessions of MBI, CBT, and HealthEd by blinded, expert reviewers to determine if ratings ≥ 8 . Chi-square analyses will be used to explore whether the percentages meeting these criteria vary across conditions (MBI vs. CBT vs. HealthEd) and site. In Aim 2, study flow will be described according to CONSORT guidelines for the reporting of clinical trials.^{176,177} Descriptive analyses will be generated to determine: (i) the percentage of adolescents who enroll after being determined to be eligible, (ii) number of months to reach recruitment goal, (iii) percentage of adolescents who attended 5 of 6 ($\geq 80\%$ sessions), (iv) percentage of adolescents whose likability/credibility ratings were ≥ 4 (1-5 scale, with 5 being the most positive valence), (v) percentage of adolescents who complete post-treatment and 1-year follow-up assessments, and (vi) percentage compliance with standardized operating procedure checklists for all assessments. Analyses of variance (ANOVA) and chi-square will be used to describe any potential differences across the 4 sites and the 3 intervention arms. A Tukey adjustment will be used to control for multiple comparisons. For the primary analyses in Aims 1 and 2, we do not plan to adjust for covariates as our interest is in estimating measures of success independent of participant characteristics.

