Administration: All three interventions will be delivered by a clinical or counseling psychologist. Programs will be co-facilitated by a graduate student in clinical or counseling psychology, social work, prevention science, or related field, or a research associate with a master's degree in clinical or counseling psychology, social work, prevention science, or related field. Psychologists and co-facilitators will participate in MBI, CBT, and HealthEd training. Sessions will be audio-recorded and reviewed weekly by [name] (MBI) and [name] (CBT, HealthEd) for adherence and competence. Feedback will be provided in weekly supervision. Facilitators with drift or deficiencies will be re-trained via "booster sessions" as needed. To minimize facilitator effects, psychologist facilitators at each site will facilitate all three programs.

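### Section 8.6.1 compares arms with chi-square and ANOVA that ignore the clustering assumed in section 8.2; the three-arm fidelity test could have a type I error anywhere from about 4% to 21%

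*Combined protocol and SAP*

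**What the plan says.** Section 8.2 justifies the sample size by the width of a 95% confidence interval. For Aim 1 it assumes that "the true proportion of sessions within an intervention arm during which fidelity criteria are met is 85" percent, with "4 clusters (one facilitator per treatment arm per site), 16 sessions per cluster" and a correlation of 0.06. It concludes that "we will have reasonable precision in our estimates of fidelity after accounting for the intraclass correlation coefficient (ICC"). For loss to follow-up it again takes "4 clusters, an average of 8 participants per cluster" and the same correlation.

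Section 8.6.1 sets the observed percentages against the benchmarks. For the Aim 1 ratings and training scores it adds: "Chi-square analyses will be used to explore whether the percentages meeting these criteria vary across conditions (MBI vs. CBT vs. HealthEd) and site". For Aim 2 it says: "Analyses of variance (ANOVA) and chi-square will be used to describe any potential differences across the 4 sites and the 3 intervention arms". It names no cluster term, design effect, robust variance or confidence interval, and it states that the primary analyses are not adjusted for covariates.

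Multilevel models that allow for site and cohort correlation appear only in section 8.6.2, for depression, insulin resistance, stress-related behavior and stress physiology. That section also plans to estimate intraclass correlations for binary variables, but it does not link them to the section 8.6.1 tests.

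Section 3.7 matters for the size of the problem: "psychologist facilitators at each site will facilitate all three programs".

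**The concern.** Chi-square and one-way ANOVA assume independent observations. Sessions led by one facilitator, and adolescents treated in one group, are not independent, and section 8.2 says so by its choice of inputs. If the correlation acts within arm-by-site cells, one weak or strong facilitator-program pairing, or one unusual group, can look like a difference between arms.

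This affects session fidelity (the Aim 1 primary outcome in sections 3.2 and 8.5.1) and three Aim 2 secondary outcomes: attendance, liking/credibility and retention. Section 1.2 says that training and procedures will be modified on the information from these objectives, so a spurious arm difference could feed into the next trial's design. In addition, the interval width on which the trial was sized is not among the results that section 8.6.1 promises.

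The chi-square in section 8.6.1 also covers post-training and mock-session scores. Those come from a small set of facilitators, each trained in all three programs (section 5.1), so the scores are paired across programs and sparse.

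**Working it through.** **Inputs from section 8.2**
- Aim 1: proportion 0.85; 4 clusters per arm; m = 16 sessions per cluster; "coefficient of variation of the number of sessions equal to 0.01".
- Aim 2: proportion 0.15; 4 clusters per arm; m = 8; coefficient of variation 0.11.
- Correlation 0.06 in both. It is printed as p and is read here as the intraclass correlation, because it reproduces the stated width.

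**Input from other sections**
- Sessions per cluster from the design: 6 sessions × 2 cohorts per site = 12 (section 3.6, Table 4 note). The revised note gives the same average: 8 cohorts × 6 sessions = 48 per arm, and 48 / 4 sites = 12.

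**Assumptions**
- Alpha is 5%; section 8.6.1 states none.
- The unit tested is the session, as in section 8.2.

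**Step 1: reproduce the plan's figure.** Design effect DE = 1 + [(1 + CV²)m − 1] × ICC.
- Aim 1: DE = 1 + (16.0016 − 1) × 0.06 = 1.90. Effective n = 64 / 1.90 = 33.7. Width = 2 × 1.96 × √(0.85 × 0.15 / 33.7) = 24.1%, against 24% stated. Without the correlation it is 17.5%.
- Aim 2: DE = 1 + (8.0968 − 1) × 0.06 = 1.43. Effective n = 32 / 1.43 = 22.4. Width = 29.6%, against 28% stated. This small difference does not affect the point.

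**Step 2: true size of the three-arm chi-square with independent arm-by-site clusters.** The statistic is inflated by about DE. With 2 degrees of freedom the size is P(χ² > 5.991 / DE) = exp[−5.991 / (2 × DE)].

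| Outcome | m | DE | Formula | Simulated |
|---|---|---|---|---|
| Session fidelity | 16 | 1.90 | 21% | 20.5% |
| Session fidelity | 12 | 1.66 | 16% | 16.2% |
| Participant outcomes | 8 | 1.43 | 12% | 11.8% |

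The simulation is beta-binomial with 200,000 trials per row. With the correlation set to essentially zero it returns 5.0%, 5.0% and 4.8%, so the excess comes from clustering. If the participant cluster is taken as a therapy group of 5, DE = 1 + 4 × 0.06 = 1.24 and the size is about 9%. For fidelity at m = 16, a correlation of 0.01 gives 7.4%, 0.03 gives 12.7% and 0.10 gives 30.2%.

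**Step 3: crossed facilitators.** If one psychologist leads all three programs at a site, a facilitator or site effect common to the arms cancels in the arm comparison. The simulated size of the three-arm fidelity test depends on how much of the correlation is shared:

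| Shared across arms | m = 16 | m = 12 |
|---|---|---|
| None | 21% | 16% |
| Half | 12% | 10% |
| All | 4.4% | 4.2% |

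For participant outcomes with all of it shared, the size is 4.2%. The documents do not say how the correlation divides.

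**Step 4: training scores.** With one lead psychologist per site there are 4 scores per program. Even at a 50% pass rate the expected count per cell is 4 × 0.5 = 2. Co-facilitators add to this, but their number is not given. The same people appear in all three columns, so the chi-square assumption fails whatever the correlation.

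**The case against.** The strongest reply is that nothing is decided by these tests. The primary outcomes are descriptive benchmarks: ratings of at least 8, and at least 80% of eligible adolescents enrolling. Section 8.6.1 uses the tests only to explore and describe, gives no alpha, and ties no revision of training to a significant result. This stands, and it limits the point to exploratory comparisons.

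It also stands that enrollment is outside the problem. Section 6.2.4 dates enrollment at randomization, before any therapy group exists. For site comparisons the site effect is partly what is being looked for, so a rejection there is not simply a false positive.

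A reader might infer that false fidelity differences are roughly tripled. That multiple fits only some inputs: a single pairwise contrast at 16 sessions (15.5%), or the three-arm test at 12 sessions. It also requires that no correlation be shared across arms. Section 8.2 does describe its clusters as specific to arm and site, but section 3.7 crosses facilitators with arms, so no single multiple can be asserted.

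A reader might also infer that the plan will publish intervals that are too narrow. It specifies no interval in section 8.6.1, so the fault is omission. The Tukey sentence can be read as applying to the ANOVA contrasts, and no point is made of it.

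**Conclusion.** The point holds as an inconsistency between sections 8.2 and 8.6.1. The data that section 8.2 treats as clustered are compared between arms by methods that assume independence.

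At an assumed 5% alpha and a correlation of 0.06, the type I error of the three-arm chi-square is:
- about 4% to 21% for session fidelity at 16 sessions per cluster;
- about 4% to 16% at 12 sessions per cluster;
- about 4% to 12% for participant outcomes at 8 per cluster.

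The lower end requires all correlation to be common to the arms; the upper end requires none to be. The plan gives no basis for assuming the favorable end, and its own precision calculation is set up as the unfavorable one.

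It would be too strong to say that section 8.6.1 contradicts section 8.2, or that the primary conclusions are at risk. One section concerns interval width and the other exploratory tests, and success is judged against thresholds. The change is worth making because it is cheap and these comparisons may inform the next trial.

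**What to change.** Amend section 8.6.1 as follows.

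1. Report each session-level and participant-level percentage with a cluster-adjusted 95% confidence interval, which is the basis on which the trial was sized, using small-sample degrees of freedom.
2. Make the exploratory arm comparisons with a method that blocks on site or facilitator and allows for therapy-group clustering. A permutation test at group level within site, or GEE with a small-sample correction, would serve. Otherwise omit the P-values.
3. Describe facilitator training and mock-session scores by program and site without chi-square.
4. State the unit of analysis for fidelity, and present site differences as descriptive.

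The cost is SAP wording and a little programming, with no new data. Intervals will be wider: with t on 3 degrees of freedom (multiplier 3.18 in place of 1.96), the Aim 1 width rises from 24% to about 39% and the Aim 2 width from about 30% to about 48%. Even then, simulated coverage for fidelity is about 92% to 93%, so the method should be checked by simulation before it is fixed.
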